5.4 General Concomitant Medication and Supportive Care Guidelines

5.4.1 Trametinib

Because there is a potential for interaction of trametinib with other concomitantly administered drugs through the cytochrome P450 system, the case report form must capture the concurrent use of all other drugs, over-the-counter medications, or alternative therapies. After discussion with the Principal Investigator, agents known to affect or with the potential to affect selected CYP450 isoenzymes may be permitted, if clinically indicated.

5.4.2 Dabrafenib

Because there is a potential for interaction of dabrafenib with other concomitantly administered drugs through the cytochrome P450 system, the case report form must capture the concurrent use of all other drugs, over-the-counter medications, or alternative therapies. The Principal Investigator should be alerted if the patient is taking any agent known to affect or with the potential to affect selected CYP450 isoenzymes. Appendix B is a patient information sheet that can be used for this specific protocol and presented to the patient.

Dabrafenib mesylate is a substrate for CYP 3A4, 2C8, p-glycoprotein (Pgp), and breast carcinoma resistance protein (Bcrp). Strong inhibitors/inducers of these enzymes and transporters are prohibited for eligibility and during the study.

Mild or moderate inhibitors/inducers of CYP 3A4, 2C8, Pgp, and Bcrp should be used with caution as dabrafenib serum concentrations may be altered. Because the lists of these agents are constantly changing, it is important to regularly consult a frequently-updated list such as <http://medicine.iupui.edu/clinpharm/ddis/table.aspx>; medical reference texts such as the Physicians' Desk Reference may also provide this information.

Dabrafenib may induce CYP 3A4, 2B6, and possibly 2C8/9 and 2C19. Use concomitant medications that are substrates of these isoenzymes with caution as there may be loss of efficacy. Substitute with other medications that are not affected if possible.

5.4.3 INCB039110

INCB039110 does not induce or inhibit the cytochrome P450 system, however the concurrent use of all other drugs, over-the-counter medications, or alternative therapies must be captured in the case report

form. *In vitro* studies indicate that CYP3A4 is the major isozyme responsible for the metabolism of INCB039110 in human liver microsomes. INCB039110 did not significantly inhibit the activity of CYP1A2, CYP2B6, CYP2C8, CYP2C9, CYP2C19, CYP2D6, and CYP3A4, suggesting that the potential for INCB039110 to cause clinical drug-drug interactions through CYP inhibition is low.

Supportive treatment should be given as per the institution standards and at the Investigator's discretion. Antiemetics, anti-diarrheal agents, etc. may be given to treat or prevent gastrointestinal toxicities.

5.5 Duration of Therapy

In the absence of treatment delays due to adverse event(s), treatment may continue until one of the following criteria applies:

- Disease progression,
- Intercurrent illness that prevents further administration of treatment,
- Unacceptable adverse event(s),
- Patient decides to withdraw from the study, or
- General or specific changes in the patient's condition render the patient unacceptable for further treatment in the judgment of the investigator.

Participants will be removed from the protocol therapy when any of these criteria apply. The reason for removal from protocol therapy, and the date the participant was removed, must be documented in the case report form (CRF). Alternative care options will be discussed with the participant.

In the event of unusual or life-threatening complications, treating investigators must immediately (within 24 hours of awareness of the event) notify the Overall PI, [name]., P.h.D at [contact], [name].

5.6 Duration of Follow Up

Participants will be followed for 2 years after removal from study treatment or until death, whichever occurs first. Participants removed from study treatment for unacceptable adverse events will be followed until resolution or stabilization of the adverse event. All patients will have a follow-up encounter 30 days (+ 3 days) after last study treatment for assessment of adverse effects. This encounter can be carried out in clinic or over the telephone. Following discontinuation of dabrafenib, monitoring for non-cutaneous secondary/recurrent malignancies should continue for up to 6 months or until initiation of another anti-neoplastic therapy. Dermatologic skin assessments should be completed every 3 months for 6 months after discontinuation of dabrafenib or initiation of another anti-neoplastic therapy. Participants' vital status will be followed every 6 months (telephone contact is adequate) following removal from the study treatment. Date and cause of death should be provided for participants who become deceased within the 2-year interval following removal from the study treatment.

5.7 Criteria for Removal from Study

Patients will be removed from study upon completion of the follow-up phase (section 5.5), death or withdrawal of consent. The reason for study removal and the date the patient was removed must be documented in the Case Report Form.

The research team updates the relevant Off Treatment/Off Study information in OnCore.

6. DOSING DELAYS/DOSE MODIFICATIONS

The criteria for dose modification of dabrafenib, trametinib, and INCB039110 are detailed below. In the setting of toxicities of sufficient severity justifying dose modification, every effort will be made to identify the related medication. In the setting where the offending agent is difficult to determine, dose modification will occur with each agent according to the specified dose modifications for each agent.

6.1 Dabrafenib or Dabrafenib + Trametinib Dose Modifications

The tables below outline the dose levels to be used for any necessary dabrafenib and trametinib dose modifications in studies which include the combination:

Current Dose Dabrafenib	If Dose Reduction Required	Reduce To
150 mg BID	→	100 mg BID
100 mg BID	→	75 mg BID
75 mg BID	→	50 mg BID
50 mg BID	→	Discontinue dabrafenib

Current Dose Trametinib	If Dose Reduction Required	Reduce To
2 mg QD	→	1.5 mg QD
1.5 mg QD	→	1.0 mg QD
1.0 mg QD	→	Discontinue trametinib

Dabrafenib + Trametinib Dose Modification Guidelines

If an AE resolves to grade 1 or baseline at the reduced dose level, and no additional toxicities are seen after 4 weeks of study treatment at the reduced dose, the dose may be increased to the previous dose level. A dose reduction below 50 mg BID for dabrafenib is not allowed. For dabrafenib-trametinib combination, dose below 1 mg once daily for trametinib is not allowed; however, if dabrafenib will be permanently discontinued for dabrafenib-related toxicities, the patients will be allowed to continue trametinib and INCB039110. Conversely, if trametinib is permanently discontinued for trametinib-related toxicities, patients will be allowed to continue dabrafenib and INCB039110.

In the event that INCB039110 needs to be discontinued due to toxicity reasons, treatment with dabrafenib and trametinib may continue at the discretion of the investigator until time of disease progression.

In the event that dabrafenib and INCB039110 need to be discontinued due to toxicity reasons, treatment with trametinib may continue at the discretion of the investigator until time of disease progression.

In the event that trametinib and INCB039110 need to be discontinued due to toxicity reasons, treatment with dabrafenib may continue at the discretion of the investigator until time of disease progression.

6.1.1 Dabrafenib or Dabrafenib + Trametinib Dose Modification for Treatment Related Toxicities Not Specified in Subsequent Sections

Table 6-1: Dabrafenib or Dabrafenib + Trametinib Dose Modification for Treatment Related Toxicities Not Specified in Subsequent Sections*

CTCAE Grade	Action and Dose Modification
Grade 1 Grade 2 (Tolerable)	
 Continue study treatment at same dose level (no dose modification). Monitor closely. Provide supportive care according to institutional standards.
Grade 2 (Intolerable) Grade 3	
 Interrupt study treatment. Monitor closely. Provide supportive care according to institutional standards. When toxicity resolves to grade 1 or baseline, restart study treatment reduced by one dose level. If the grade 2 (intolerable) or grade 3 toxicity recurs, interrupt study treatment. When toxicity resolves to grade 1 or baseline, restart study treatment reduced by another dose level. If dabrafenib must be reduced to <50 mg BID, permanently discontinue dabrafenib If trametinib must be reduced to < 1.0 mg QD, permanently discontinue trametinib
Grade 4	
 Permanently discontinue or interrupt study treatment. Monitor closely. Provide supportive care according to institutional standards. If study treatment was interrupted, restart with study treatment reduced by one dose level once toxicity resolves to grade 1 or baseline. If dabrafenib must be reduced to <50 mg BID, permanently discontinue dabrafenib If trametinib must be reduced to < 1.0 mg QD, permanently discontinue trametinib

*If the AEs are thought to be due to one of the two agents, resumption of the other agents may be considered if the first agent is discontinued due to toxicities and treatment interruption is <28 days.

6.1.2 Dabrafenib or Dabrafenib + Trametinib Dose Modification for Pyrexia Suspected to be Treatment-Related

- Pyrexia is defined as a body temperature equal to or above 38.5° Celsius or 101.3° Fahrenheit
- Pyrexia is an adverse event associated with dabrafenib, and is increased in frequency and severity in subjects receiving dabrafenib in combination with trametinib. In a minority of cases, pyrexia was accompanied by symptoms such as severe chills/rigors, dehydration, hypotension, dizziness or weakness and required hospitalization.

Subjects should be instructed on the importance of immediately reporting febrile episodes. In the event of a fever, the subject should be instructed to take anti-pyretics (e.g. ibuprofen or acetaminophen/paracetamol) as appropriate to control fever. The use of oral corticosteroids

should be considered in those instances in which anti-pyretics are insufficient. Monitor serum creatinine and other evidence of renal function during and following severe events of pyrexia.

Table 6-2: Dabrafenib or Dabrafenib + Trametinib dose Modification and Management Requirements for Pyrexia Suspected to be Related to Treatment

Event	Management Guideline	Dose Modification
Work up:		

 Clinical evaluation for infection and hypersensitivity, especially if pyrexia is complicated by rigors, severe chills, dehydration, etc. Laboratory work-up (must include full-blood-count, electrolytes, creatinine, BUN, CRP, liver-function tests, blood and urine culture). 		
Management:		
	
 Anti-pyretic treatment should be started immediately at the first occurrence. Anti-pyretic treatment may include acetaminophen (paracetamol), ibuprofen, or suitable anti-pyretic medication per institutional standards. Oral hydration is encouraged in subjects without evidence of dehydration. Intravenous hydration is recommended if pyrexia is complicated by dehydration/hypotension. In subject experiencing pyrexia complicated by rigors, severe chills, etc., which cannot be controlled with anti-pyretic medication, oral corticosteroids should be started. Prophylactic anti-pyretic treatment is recommended after the 2nd event if pyrexia , or after the 1st event if complicated by rigors or severe chills. Prophylactic anti-pyretics may be discontinued after three days in absence of pyrexia. 	
1st Event:	
 Clinical evaluation for infection and hypersensitivity Laboratory work-up Hydration as required Administer anti-pyretic treatment if clinically indicated and continue prophylactic treatment 	
 Interrupt dabrafenib. Continue trametinib. Once pyrexia resolves to baseline, if fever was associated with rigors, dehydration, hypotension, or renal insufficiency, reduce dabrafenib by one dose level. If it was not, restart dabrafenib at the same dose level.
2nd Event	
 Clinical evaluation for infection and hypersensitivity^c Laboratory work-up^c Hydration as required^d Within 3 days of onset of pyrexia: 
 Optimize anti-pyretic therapy. Consider oral corticosteroids (i.e., prednisone 10 mg) for at least 5 days or as clinically indicated.^f 	
 Interrupt dabrafenib. Continue trametinib. Once pyrexia resolves to baseline, if fever was associated with rigors, dehydration, hypotension, or renal insufficiency, reduce dabrafenib by one dose level. If it was not, restart dabrafenib at the same dose level.

Table 6-2: Dabrafenib or Dabrafenib + Trametinib dose Modification and Management Requirements for Pyrexia Suspected to be Related to Treatment

Event	Management Guideline	Dose Modification
Subsequent Events:	
 • Clinical evaluation for infection and hypersensitivity • Laboratory work-up • Hydration as required • Blood sample for cytokine analysis^e • Within 3 days of onset of pyrexia: 
 – Optimize oral corticosteroid dose as clinically indicated for recalcitrant pyrexia.^g – If corticosteroids have been tapered and pyrexia recurs, restart steroids. – If corticosteroids cannot be tapered, consult medical monitor. 	
 • Interrupt dabrafenib. • Continue trametinib. • Once pyrexia resolves to baseline, restart dabrafenib reduced by one dose level.^a • If dabrafenib must be reduced to <50 mg BID, permanently discontinue dabrafenib.

^a Dabrafenib should be reduced by one dose level after three episodes of pyrexia which cannot be managed by best supportive care and increasing doses of oral steroids. Escalation of dabrafenib is allowed if no episode of pyrexia is observed in the 4 weeks subsequent to dose reduction.

6.1.3 Dabrafenib or Dabrafenib + Trametinib Dose Modification for **Rash Suspected to be Related to Treatment**^a

Rash is a frequent AE observed in patients receiving trametinib, dabrafenib, or the combination of both therapies. Recommendations for supportive care and guidelines for dose modifications for rash are based on experience with other MEK inhibitors and EGFR inhibitors (Balagula *et al.*, 2010; Lacouture *et al.*, 2011).

Table 6-3: Dabrafenib or Dabrafenib + Trametinib Supportive care and Dose Modification for Rash Suspected to be Related to Treatment

CTCAE Grade	Adverse Event Management	Action and Dose Modification
The following Rash prophylaxis is recommended for the first 6 weeks of study treatment:		

 • Avoid unnecessary sun light • Apply broad-spectrum sunscreen (containing titanium dioxide or zinc oxide) with a skin protection factor (SPF) ≥ 15 at least twice daily. • Use thick, alcohol-free emollient cream (e.g., glycerine and cetomacrogol cream) on dry areas of the body at least twice daily. 		
Symptom Management 
 • Pruritic lesions: cool compresses and oral antihistamines therapies. • Fissuring lesions: Monsel's solution, silver nitrate, or zinc oxide cream. • Desquamation: thick emollients and mild soap. • Paronychia: antiseptic bath, local potent corticosteroids in addition to oral antibiotics; if no improvement, consult dermatologist or surgeon • Infected lesions: appropriate bacterial/fungal culture-driven systemic or topical antibiotics. 		
* Subjects who develop rash/skin toxicities should be seen by a qualified physician and should receive evaluation for symptomatic/supportive care management		
Grade 1	
 • If not yet started, initiate prophylactic and symptomatic treatment measures.¹ • Use moderate strength topical steroid.² • Reassess within 2 weeks. 	
 • Continue study treatment. • If rash does not recover to baseline within 2 weeks despite best supportive care, reduce study treatment by one dose level.³
Grade 2 (tolerable)	
 • If not yet started, initiate prophylactic and symptomatic treatment measures.¹ • Use moderate strength topical steroid.² • Reassess within 2 weeks. 	
 Reduce study treatment by one dose level. • If rash recovers to \leq grade 1 within 2 weeks, increase dose to previous dose level. • If no recovery to \leq grade 1 within 2 weeks, interrupt study treatment until recovery to \leq grade 1. Restart study treatment at reduced dose level.
Grade ≥ 3 or intolerable Grade 2	
 • Use moderate strength topical steroids PLUS oral methylprednisolone dose pack.² • Consult dermatologist. 	
 • Interrupt study treatment until rash recovers to \leq grade 1. Restart with study treatment reduced by one dose level.³ 
If no recovery to \leq grade 2 within 28 days, permanently discontinue study treatment.

1. Rash prophylaxis is recommended for the first 6 weeks of study treatment. 2. Moderate-strength topical steroids: Triamcinolone 0.1% cream or ointment or Fluticasone propionate 0.05% cream or 0.005% ointment. 3. Study treatment may be escalated to previous dose level if no rash is evident 4 weeks after restarting study treatment.		

6.1.4 Dabrafenib or Dabrafenib + Trametinib Dose Modification for palmar-plantar erythrodysesthesia syndrome (PPES)

- Lifestyle modification: avoidance of hot water, traumatic activity, constrictive footwear, or excessive friction on the skin and the use of thick cotton socks and gloves, and shoes with padded insoles
- Symptomatic treatments: apply moisturizing creams frequently, topical keratolytics (e.g. urea 20-40 % cream, salicylic acid 6%, tazarotene 0.1% cream, fluorouracil 5% cream), clobetasol propionate 0.05% ointment for erythematous areas, topical lidocaine 2%, and / or systemic pain medication such as nonsteroidal anti-inflammatory drugs, codeine, and pregabalin for pain.

Dose modification may also be required. – Refer to section 1.2 for dose modification.

6.1.5 Dabrafenib or Dabrafenib + Trametinib Dose Modification for New Primary/ Recurrent Malignancies:

- Cutaneous SCC and New Primary Melanoma

Dermatologic skin assessments for subjects on treatment should be performed before initiation of dabrafenib, then every 2 months through treatment. Skin exams should continue every 2-3 months for 6 months after discontinuation of dabrafenib or initiation of another anti-neoplastic therapy.

Cutaneous SCC

Cases of cuSCC (which include those classified as keratoacanthoma or mixed keratoacanthoma subtype) have been observed in subjects treated with dabrafenib. Approximately 70 % of events occurred within the first 12 weeks of treatment with a median time to onset of 8 weeks.

These should be surgically removed according to institutional practices. Dose modification or interruption of study treatment is not required for cuSCC or KA, however cuSCC should be reported as an SAE.

Patients should be instructed to immediately inform their physician if new lesions develop.

New Primary Melanoma

New primary melanomas have been reported in patients treated with dabrafenib. These were identified primarily within the first 5 months of therapy and did not require treatment modification other than excision.

- Non-Cutaneous Malignancies

In vitro experiments have demonstrated paradoxical activation of MAP-kinase signalling in BRAF wild type cells with RAS mutations when exposed to BRAF inhibitors, which may lead to increased risk of non-cutaneous malignancies in patients treated with dabrafenib. Cases of RAS-driven malignancies have been seen with BRAF inhibitors. Patients should be monitored as clinically appropriate.

Permanently discontinue dabrafenib in patients who develop RAS mutation-positive non-cutaneous malignancies. If used in combination with trametinib, trametinib may continue.

Following discontinuation of dabrafenib, monitoring for non-cutaneous secondary/recurrent malignancies should continue for up to 6 months or until initiation of another anti-neoplastic therapy.

New non-cutaneous malignancies should be reported as a SAE. A biopsy of the new malignancy should be taken.

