6.1.9 Dabrafenib + Trametinib Dose Modification for Renal Insufficiency

Cases of renal insufficiency have occurred in patients receiving the combination of dabrafenib and trametinib. Prior to start of study treatment, concomitant medications should be reviewed for the potential risk of inducing nephrotoxicity and modified if clinically possible.

Table 6-5: Dabrafenib or Dabrafenib + Trametinib Dose Modification for Renal Insufficiency

Serum Creatinine Level	Management Guideline	Action and Dose Modification

Serum creatinine increase >0.2 mg/dL (18 mcmol/L)
 
BUT
 
≤0.5 mg/dL (44 mcmol/L) above baseline
	
• Recheck serum creatinine within 1 week.• If elevation persists beyond 4 weeks, recommend evaluation (consider renal biopsy) for etiology; consider nephrology consultation.• If pyrexia is present, treat pyrexia as per guidelines.^a	Continue study treatment at the same dose level.

Table 6-5: Dabrafenib or Dabrafenib + Trametinib Dose Modification for Renal Insufficiency

Serum Creatinine Level	Management Guideline	Action and Dose Modification
Serum creatinine increase >0.5 mg/dL (44 μmol/L)	
Monitor serum creatinine ≥2-times per week.Hospitalization may be necessary if serum creatinine cannot be monitored frequently.If pyrexia is present, treat pyrexia per guidelines.^aConsult nephrologist if clinically indicated.Perform renal biopsy if clinically indicated, for example:
Renal insufficiency persists despite volume repletion.Patient has new rash or signs of hypersensitivity (such as elevated eosinophil count).	
Interrupt study treatment until serum creatinine recovers to baseline.Restart study treatment.^b

^a NSAIDs can induce renal insufficiency, especially in patients with dehydration; encourage oral fluids or consider IV fluids as clinically indicated. See guidelines for pyrexia Section 6.1.2.

^b Investigator may restart at either the same or a reduced dose level. Escalation of study treatment to previous dose level is allowed if another episode of renal insufficiency does not occur after 4 weeks of dose reduction.

6.1.10 Dabrafenib + Trametinib Dose Modification for **Reduced Left Ventricular Ejection Fraction**

Decreases of the left ventricular ejection fraction (LVEF) have been observed in patients receiving dabrafenib plus trametinib.

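### For treatment-related fever with a creatinine rise above 0.5 mg/dL, Table 6-2 continues trametinib while Table 6-5 holds it; Table 6-2 should say that the hold applies

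*Combined protocol and SAP*

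**What the plan says.** **Fever (Section 6.1.2, Table 6-2).** The dose-modification column opens the same way for first, second and subsequent events: "Interrupt dabrafenib. Continue trametinib". The first- and second-event rows then provide for complicated fever, including fever with renal insufficiency: "Once pyrexia resolves to baseline, if fever was associated with rigors, dehydration, hypotension, or renal insufficiency, reduce dabrafenib by one dose level". The subsequent-events row says "Once pyrexia resolves to baseline, restart dabrafenib reduced by one dose level". The text before the table adds "Monitor serum creatinine and other evidence of renal function during and following severe events of pyrexia", and creatinine is part of the required laboratory work-up. The text shown does not send the reader on to the renal table.

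**Creatinine (Section 6.1.9, Table 6-5).** The table covers dabrafenib alone or with trametinib.

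- Rise above 0.2 and up to 0.5 mg/dL: "Continue study treatment at the same dose level".
- Rise above 0.5 mg/dL, action column: "Interrupt study treatment until serum creatinine recovers to baseline". Footnote b lets the investigator restart at the same or a lower level.
- Rise above 0.5 mg/dL, management column: "If pyrexia is present, treat pyrexia per guidelines". Footnote a adds "See guidelines for pyrexia Section 6.1.2".

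**The concern.** A febrile patient whose creatinine rises by more than 0.5 mg/dL falls under both tables. Table 6-2 does not overlook this patient: two of its rows name renal insufficiency and still leave trametinib running. An investigator who manages the episode from Table 6-2 would follow a written instruction to continue a drug that Table 6-5 says to hold. Another investigator, starting from Table 6-5, would hold it.

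The overlap is foreseeable. The renal failure paragraph of Section 2.3.2.4 reports that acute renal failure on the doublet mostly arose during fever with dehydration, alongside or instead of other risk factors. What is at stake is consistent and safe handling of trametinib while the kidneys are impaired.

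**Working it through.** No power, sample-size or error-rate formula applies. The check sets the two tables side by side for one patient: treatment-related fever and a creatinine rise above 0.5 mg/dL.

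| Item | Table 6-2 (fever) | Table 6-5 (rise above 0.5 mg/dL) | Can both be met? |
|---|---|---|---|
| Trametinib during the event | Continue | Hold | **No** |
| Dabrafenib during the event | Hold | Hold | Yes |
| Condition for dabrafenib restart | Fever back to baseline | Creatinine back to baseline | Yes: wait for both |
| Dabrafenib level at restart | One level lower (renal branch of rows 1-2; subsequent-events row) | Same or lower (footnote b) | Yes: one level lower |
| Trametinib level at restart | No rule, as it is not stopped | Same or lower (footnote b) | Yes |

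Only the trametinib line conflicts. At rises of 0.5 mg/dL or less there is no trametinib conflict, because both tables continue it.

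**Possible tie-breakers elsewhere**

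- Section 6, opening paragraph: deals with doubt about which drug caused a toxicity, not with two tables that apply to one episode.
- Section 6.1.1, Table 6-1: limited to toxicities without their own section. Fever and renal insufficiency each have one.
- Section 5.1.4: sends creatinine to the Section 6.1.9 table, but only for Day 1 of Cycle 2 onward. It shows which table is meant to decide treatment on creatinine; it does not cover Cycle 1 or a mid-cycle fever.
- Table 6-5, footnote a: points to Section 6.1.2, and so back to the instruction to continue trametinib.

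**What the documents offer on frequency (Section 2.3.2.4)**

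- Renal failure in the 150/2 arm: 7%, with n = 55 from the adverse event table. Since 3/55 = 5.5%, 4/55 = 7.3% and 5/55 = 9.1%, this is 4 patients.
- Serious non-infectious febrile events complicated by hypotension, dehydration, severe rigors or chills, or renal failure: 10/404 = 2.5% (exact 95% CI 1.2% to 4.5%). Renal failure is one of four complications, so its share is 10/404 or less. Non-serious fever, and creatinine rises not reported as renal failure, are left out.

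Neither figure is the rate of fever with a creatinine rise above 0.5 mg/dL.

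**The case against.** The strongest reply is that the tables add up. Section 6.1 gives each toxicity its own table, so the trametinib line in Table 6-2 states only what fever requires and does not cancel a hold that another toxicity requires. The row of Table 6-5 for rises above 0.5 mg/dL supports this: fever appears in its management column, and the action column still orders the hold. Table 6-9 works in the same way, since fever makes diarrhea complicated and study treatment is interrupted without any pointer to Table 6-2. Creatinine is checked during the fever work-up, so the rise would be found.

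Most of this stands. The additive reading is the natural one, and many investigators would reach it. It does not remove the point, because Table 6-2 names renal insufficiency itself and still says to continue trametinib. The reader has to infer that the instruction gives way.

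A second reply is that Table 6-2 cites footnotes c to g whose text is not shown, so a renal pointer could sit there. That limits any claim that no link exists. The citations are in the management column, at work-up, hydration, cytokine and steroid items, and not at the trametinib instruction.

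Three stronger readings are tempting, but the documents do not support them:

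- *The tables also clash on dabrafenib.* They do not. Both restart conditions can be met, and a one-level reduction satisfies both tables.
- *Past practice on the doublet favoured holding trametinib.* Section 2.3.2.4 reports one permanent discontinuation and three dose interruptions for renal events. It does not say which drug was interrupted in those three, or whether these subjects had fever.
- *The 2.5% figure measures the problem.* It is a composite with an unknown renal share and no creatinine threshold. Applied to the maximum enrolment of 38 (Section 13.2), it gives 38 x 10/404 = 0.9 patients for the whole composite, not for this overlap.

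**Conclusion.** The point holds for trametinib only, and only when treatment-related fever coincides with a creatinine rise above 0.5 mg/dL. There Table 6-2 and Table 6-5 give opposite instructions. Table 6-5 is the better rule, but the text shown does not say that it prevails.

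This rests on two assumptions. First, study treatment in Table 6-5 includes trametinib, as its title indicates. Second, the unseen footnotes to Table 6-2 do not qualify the trametinib instruction.

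The size cannot be stated, because the documents give no rate for this overlap; they show only that it is foreseeable. A reader might infer an effect on dose finding, since Section 5.3 counts toxicity that leads to more than 20% of doses being missed. The documents give no basis for sizing such an effect, and none on the MTD or the analysis is claimed. This is a minor patient-safety correction.

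**What to change.** In the dose-modification column of Table 6-2, in all three rows, replace the trametinib instruction with wording such as:

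> Continue trametinib, unless creatinine rises >0.5 mg/dL above baseline; then also follow Table 6-5: interrupt trametinib as well, and restart only when both fever and creatinine have returned to baseline. Restart dabrafenib reduced by one dose level as this table requires; restart trametinib at the same or a reduced level per Table 6-5 footnote b.

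This keeps the Table 6-2 rule for the dabrafenib level and the Table 6-5 rule for the trametinib level, so neither table is overridden on restart dose. It does not address INCB039110, which neither table names.

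The cost is a short amendment and somewhat more trametinib interruption, which Table 6-5 already orders. Because Table 6-5 sets no maximum hold, slow creatinine recovery could lengthen it.

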1.2 Study Design

The primary objective of the dose escalation component of the study is to define the maximum tolerated dose (MTD) of the triple combination of dabrafenib, trametinib, and INCB039110. The table below summarizes the planned dose levels. Dose escalation will follow a standard 3+3 design beginning in dose level 1. The doses of dabrafenib and trametinib for Dose Level 1 were selected based upon the results of the phase I study showing excellent tolerability and safety, and that this combination appears to be associated with a reduced incidence and severity of *some* of the toxic effects of monotherapy with either a BRAF or MEK inhibitor, as well as excellent clinical activity. ([name] *et al.* 2012).

Dose Level	Dabrafenib [BID/PO]	Trametinib [QD/PO]	INCB039110 (mg QD)
-2	75 mg	1 mg	100 mg
-1	150 mg	2 mg	100 mg
1	150 mg	2 mg	200 mg
2	150 mg	2 mg	300 mg
3	150 mg	2 mg	400 mg

It is conceivable that additional cohorts may be necessary to pick an optimal treatment regimen with the three agents. As such, if toxicity is seen at a dose level where dose modification is necessary and the prior, lower dose level was treated without DLT, then additional dose cohorts between the two dose levels will be considered (see section 6 for details of this process). If the toxicity is determined to be related to dabrafenib (i.e. palmar-plantar erythrodysesthesia syndrome, arthralgia) then the dose of dabrafenib will be reduced first to 75 mg BID and then increased to 100 mg BID if that first dose level is tolerated. If the toxicity is determined to be related to trametinib, then the dose of trametinib will be reduced to 1 mg QD (if a dose higher than 1 mg QD is being evaluated in the dose cohort) and then increased to 1.5 mg QD if that first dose level is tolerated. Please see section 6.1 for dose modifications of dabrafenib and trametinib. If the toxicity is determined to be related to INCB039110 then the dose will be reduced by 1 dose cohort. At the end of the planned enrollment to the phase 1 portion of the study, a complete review of the PK data and safety will occur before cohort expansion at the MTD.

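### For a patient with PPES, Section 6.1.4 points to cohort-level wording in Section 1.2 whose dabrafenib order differs from the Section 6.1 table, and nothing says which governs

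*Combined protocol and SAP*

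**What the plan says.** Three places bear on the dose of dabrafenib after PPES.

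- **Section 6.1.4** covers supportive care for a patient with PPES and notes that a dose change may also be needed. On the dose itself it says only: "Refer to section 1.2 for dose modification".
- **Section 1.2 (Study Design)** discusses adding dose cohorts between two planned levels. Within that discussion it opens a rule with "If the toxicity is determined to be related to dabrafenib (i.e. palmar-plantar erythrodysesthesia syndrome, arthralgia" and says the dabrafenib dose "will be reduced first to 75 mg BID and then increased to 100 mg BID if that first dose level is tolerated". It then sends the reader to Section 6.1 for dabrafenib and trametinib dose modifications.
- **Section 6.1** introduces its tables with "The tables below outline the dose levels to be used for any necessary dabrafenib and trametinib dose modifications in studies which include the combination". The dabrafenib table starts "150 mg BID → 100 mg BID", then "100 mg BID → 75 mg BID", then 75 to 50 mg BID, then discontinuation.

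Table 6-1, the general grade-based table in Section 6.1.1, is limited by its title to treatment-related toxicities that later sections do not deal with.

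**The concern.** Section 6.1.4 manages an individual patient. Its only dose instruction leads to a rule that names PPES and goes down to 75 mg BID and then up. The table that opens Section 6.1 goes to 100 mg BID and then down, and makes no exception for PPES. A site that follows the pointer literally and a site that uses the table would treat the same toxicity differently.

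At stake is consistency of dabrafenib dosing after a named toxicity. Section 13.3.1 plans to take dose reductions into account when exploring efficacy, in an expansion cohort of up to 20 patients. If the size of a reduction depends on which section a site happened to read, that information is harder to interpret.

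**Working it through.** No sample-size, power or error-rate figure is involved. The check is a comparison of texts, with simple arithmetic on the doses.

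**Step 1: where the pointer leads.** The main protocol's Section 1.2 is the only sensible target. Appendix E also has a heading numbered 1.2, but it lists prohibited medications and contains no PPES rule.

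**Step 2: the two sequences side by side, from 150 mg BID.**

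| | Section 1.2 | Section 6.1 |
|---|---|---|
| Unit the text is written for | Intermediate dose cohort | Individual patient |
| PPES named? | Yes, as an example | No, but covers any necessary modification |
| First step | 75 mg BID | 100 mg BID |
| Next move in the sequence | Up to 100 mg BID | Down to 75 mg BID if a further reduction is required |
| Condition for going back up | First level tolerated | Event at grade 1 or baseline and no further toxicity after 4 weeks; return to the previous level |

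**Step 3: size of the first-step difference.**

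- Starting dose: 2 × 150 = 300 mg/day.
- Section 1.2: 2 × 75 = 150 mg/day, a cut of (300 − 150)/300 = 50%.
- Section 6.1: 2 × 100 = 200 mg/day, a cut of (300 − 200)/300 = 33%.
- Ratio: 150/200 = 0.75, so the first-step dose under Section 1.2 is 25% lower.

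**Step 4: is there a fallback?** Table 6-1 would supply a grade-based rule, but PPES has its own later section, so on its title Table 6-1 does not apply. Rash, pyrexia, hemorrhage and diarrhea each have their own modification table; PPES has only the pointer. Section 1.2 refers back to 6.1, so the path runs from 6.1.4 to 1.2 to 6.1, and no sentence says where a reader should stop.

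**Step 5: how many patients.** The dabrafenib monotherapy table in Section 2.3.2.4 (n = 187) gives PPES in 20% at any grade and 2% at grade 3-4. If those rates applied unchanged to 20 expansion patients, the counts would be 0.20 × 20 = 4 with any PPES and 0.02 × 20 = 0.4 with grade 3-4. Both probably overstate the number, because the same section reports a decrease in PPES with the combination relative to dabrafenib alone. The documents give neither a combination rate nor the rate of intolerable grade 2 PPES, so the number needing a reduction cannot be computed.

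**The case against.** The strongest answer is that the two texts govern different things. Section 1.2 is about building cohorts: its neighbouring sentences speak of a dose being evaluated in a cohort and of lowering INCB039110 by one cohort. Section 5 makes any intermediate level conditional on an IRB-approved amendment. Testing a lower intermediate cohort and then a higher one is a coherent plan and need not match a patient's step-down table. Because Section 1.2 sends the reader on to 6.1, the path can also be read as a detour that ends at the patient table.

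Much of this stands. A reader might infer that Sections 1.2 and 6.1 flatly contradict each other; taken alone, they do not. The conflict arises only because 6.1.4 sends patient management to cohort wording that names PPES. The answer does not remove the faulty pointer, and the detour reading is one of two available, since no sentence says the 6.1 table prevails.

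Three further inferences go beyond the documents:

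- **That about 4 of 20 patients would be dosed inconsistently.** Four is a monotherapy count of any PPES, not of patients needing a reduction.
- **That sites will diverge.** The text shows that they could.
- **That the MTD, or a regimen meant to stay fixed, is compromised.** Section 5.3 scores DLTs in cycle 1 by grade, specified events and missed doses, not by the size of a reduction step. Sections 5.2, 6.1 and 6.2 expressly allow each agent to be reduced or stopped.

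**Conclusion.** The point holds as an internal inconsistency that is wrong as written, and it is minor. For an individual patient with PPES the protocol supports two dabrafenib sequences, 150 against 200 mg/day at the first step with opposite next moves, and does not say which governs. This rests on reading the 6.1.4 reference as pointing to the main protocol's Section 1.2 and on taking the title of Table 6-1 at its word. If the sponsor intended Section 1.2 for cohorts only, the reference in 6.1.4 is itself the error and PPES is left without a dose rule in its own section.

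Few patients are likely to be affected, and the effect on MTD determination is small. The likely cost is some avoidable variation in dabrafenib dose among the few who need a reduction for PPES.

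**What to change.** Reconcile Sections 1.2, 6.1 and 6.1.4 so that a single reduction and re-escalation sequence applies to an individual patient with PPES, and correct the cross-reference in 6.1.4 to point to it. If the Section 1.2 wording is meant only for intermediate dose cohorts, say so there. That clarification would also cover the trametinib sentence in 1.2, which has the same pattern (1 mg QD, then 1.5 mg QD) against the 6.1 table (2 to 1.5 to 1.0 mg QD). Which sequence applies is a clinical decision for the sponsor, and this review does not propose one.

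The cost is one corrected reference and, at most, a clarifying sentence. No design, sample-size or analysis change follows.
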